Trial design and methods:	The trial consists of two non-randomised intervention substudies with before and after comparison (outpatient and inpatient), with embedded qualitative substudies involving clinician interviews and (in the outpatient setting only) observed consultations and patient interviews. Clinicians will be recruited, consented and provided with training to use the MiADE system. The system will be switched on at a particular time point, and clinical records for patients seen before and after the system was switched on will be compared. The primary outcome will be the comparison of the number of diagnoses, medication and allergies entered in a structured way per	

	patient. A rapid ethnography-based approach will be used to observe a subset of patient consultations to find out how clinicians are using the system, and semi-structured interviews will be held with patients and clinicians to understand the effect of social, cultural and behavioural information on human experiences and practices.
Trial duration per participant:	5 months
Key Study milestones	Jul 2023: Clinician recruitment and consent
	Aug 2023: Training of clinicians, surveys and observed consultations without MiADE
	Sep 2023: MiADE switch on
	Oct 2023: Interviews, surveys and observed consultations with MiADE
	Nov 2023: Study end
	Dec 2023 – Jan 2024: Data analysis
Estimated total trial duration:	7 months
Planned trial sites:	Single-site, UCLH
Total number of	Outpatient study:
participants planned:	Clinicians using MiADE: at least 25, target 50
	Patients for analysis of pseudonymised health record: estimated 3000 (assuming 25 clinicians each see 5 new patients per week, and 24 weeks of data are analysed)
	Clinicians for observed consultations and interview: 5
	Patients for observed consultation and interview: at least 20 (10 before MiADE, 10 after MiADE)
	Inpatient study:
	Clinicians using MiADE: at least 25, target 50
	Patients for analysis of pseudonymised health record: estimated 600 (assuming 5 inpatient teams each discharge 5 patients per week, and 24 weeks of data are analysed)
Main inclusion/exclusion criteria:	Electronic health record of patients being seen in clinics under the care of participating clinicians
Statistical methodology	Outpatients: comparison (pre- and post-intervention) of mean

Feasibility study of 'MiADE' point of care natural language processing, EDGE number 157134, IRAS number 322887, Protocol, Version 1.1, DATE 24/07/2023

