Consultants and specialty doctors who see outpatients will be recruited via institutional communications and networks. Interested clinicians will be consented and receive training on the use of the system, as described below. They will be asked to fill in a survey on their level of experience and comfort with EHR systems. They will have the MiADE system switched on within their EHR user profile so that they have access to it from a particular date. Electronic health records of outpatients in the clinics linked to the clinician will be assessed for 3 time periods: pre-study (before the training session), between the training session and MiADE switch-on, and for 8 weeks after MiADE is switched on. The crude number of entries per patient in the problem list, medication record and allergy record will be calculated for outpatients seen by the clinician during each interval.

Embedded qualitative substudy

For each clinician in the qualitative substudy, a sample of at least 2 outpatient consultations will be observed before the MiADE system is switched on for the clinician, and at least 2 outpatient consultations will be observed after the MiADE system is switched on. For each observed consultation, consent will be sought from the patient prior to the consultation. The researcher will sit in the consultation and observe the overall consultation, as well as timing the overall consultation and how long the clinician spends interacting with the EHR. The researcher will ask questions to the clinician after the consultation, if necessary, in order to clarify any behaviours observed.

Patient interviews

A semi-structured interview will be held with the patient after the consultation either in person (if clinic space is available) or by telephone, to explore the patient's perception and experience of the consultation.

The interview guide will include questions such as:

- How did you feel about the way that the doctor interacted with the computer in your consultation?
- How did this compare with your experience of previous consultations in this hospital or elsewhere?
- Use and usefulness of the UCLH patient portal (MyCare): prompts include
 - Access to medical diagnoses, allergies and medications on the UCLH patient portal
 - Usefulness of the features
 - Completeness and accuracy of the information
- Would you be interested in being invited to future workshops or other activities to help improve electronic health records?

Study 2 (Inpatient study)

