5.1 Inclusion criteria

Study 1 clinician inclusion criteria: Any interested clinicians who have their own clinic list at UCLH and see outpatients, who consent to be part of the study. A subset of at least 5 clinicians will be purposively sampled to include a range of specialties for the observation substudy, and they will undergo observed consultations.

Study 1 patient inclusion criteria: All outpatients seen by the clinician from 2 months before being consented until 2 months after the MiADE system is switched on for included clinicians. For clinicians selected for observation (at least 5), we will observe at least 2 consultations from one or more clinics before and 2 consultations from one or more clinics after the MiADE system is switched on will be observed. Hence the minimum number of observed consultations will be 20.

Feasibility study of 'MiADE' point of care natural language processing, EDGE number 157134, IRAS number 322887, Protocol, Version 1.1, DATE 24/07/2023

Study 2 clinician inclusion criteria: All clinicians within interested inpatient teams at UCLH.

Study 2 patient inclusion criteria: All inpatients managed under the care of a participating team during the study period.

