7.2 Registration/Randomisation Procedures (delete as appropriate) (if applicable)

Clinician participant registration will be undertaken centrally by the coordinating trial team. Clinician login names for the electronic health record system will be recorded on the study database within the UCLH system. For patients for observed consultations, the clinic code of the clinic they attend

and the time and date of their appointment will be recorded on the study database. All data will be stored on UCLH servers.

There are no randomisation procedures as this is a single-arm intervention study with before and after comparison.

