9.1 Confidentiality

The study is compliant with the requirements of the General Data Protection Regulation (2016/679) and the UK Data Protection Act (2018). All Investigators and study site staff will comply with the requirements of the General Data Protection Regulation (2016/679) with regards to the collection, storage, processing and disclosure of personal information, and will uphold the Act's core principles.

UCL is the data controller; the UCL Data Protection Officer is [contact]. The data processors are [name] (PI), [name] (software developer), [name] (software developer), [name] (researcher) and other members of the Trial Management Group. The study will be collecting the following personal data:

- Consent forms from patients and clinicians
- Survey responses from clinician participants, collected electronically
- Researcher notes observing consultations
- Notes, transcripts and recordings of interviews with patients and clinicians
- Patient information from patients under the care of the clinic code or under the care of an inpatient team participating in the study will be extracted for analysis of completeness of data. The extract will be pseudonymised and will contain minimal data that is required to answer the research questions.

Paper records will be stored in a secure filing cabinet. Electronic study records will be stored on UCLH servers or in the UCL data safe haven, which has been certified to the ISO27001 information security standard and conforms to NHS Digital's Information Governance Toolkit.

The Case Report Forms (CRFs) will not bear the participant's name or other personal identifiable data. For patients in the qualitative study, the patient's clinic code, appointment time and trial identification number will be used for identification and this will be clearly explained to the patient in the patient information sheet. Patient consent for this will be sought.

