10.6.2 Primary outcome analysis

For the outpatient study, multilevel Poisson regression will be used to calculate the ratio of counts of structured data entries between pre-MiADE and post-MiADE, with the clinician (clinic code) as a random effect to account for clustering by clinician. This analysis will also yield an estimate of the variability of the effect by clinician.

For the inpatient study, the primary outcome will be the difference in proportion of ICD-10 coded diagnoses recorded in the problem list comparing pre-MiADE and post-MiADE. This measure will be calculated separately for each inpatient team and then summarised as an overall difference in proportions, combining data from the different teams. For the inpatient study it will not be possible to differentiate results from patients seen by different clinicians within a team.

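### Study 1 identifies its records by clinic code in some sections and by the participating clinician in others; if clinic code governs, patients without MiADE exposure could enter the post-MiADE period

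*Protocol*

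**What the plan says.** Four places identify Study 1 records, or the cluster, by clinic or clinic code:

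- Study Summary, main inclusion/exclusion criteria: "Electronic health record of patients being seen in clinics under the care of participating clinicians".
- Section 4, Study 1: "Electronic health records of outpatients in the clinics linked to the clinician will be assessed for 3 time periods".
- Section 9.1, on what is extracted: "Patient information from patients under the care of the clinic code".
- Section 10.6.2, primary model: "with the clinician (clinic code) as a random effect to account for clustering by clinician".

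Other places go by the participating clinician:

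- Section 4, Study 1, on how entries per patient are counted: "will be calculated for outpatients seen by the clinician during each interval".
- Section 5.1, patient inclusion: "All outpatients seen by the clinician from 2 months before being consented until 2 months after the MiADE system is switched on".
- Section 3.3 and the statistical methodology row of the Study Summary, which attribute the structured entries to the clinician.
- Section 9.4, which describes the pseudonymised data as coming from patients treated by study clinicians.

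Section 10.1 compares time periods without saying whose entries count, so it does not decide between the two. Section 4 states that MiADE is turned on through permissions held by each clinician, in that clinician's EHR user profile. Section 5.1 admits only clinicians with their own clinic list. Section 7.2 adds: "Clinician login names for the electronic health record system will be recorded on the study database".

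**The concern.** Exposure belongs to a person, while the extract and the cluster unit belong to a clinic code. The two pick out the same patients only if the participant sees everyone booked under the code. If a colleague without MiADE sees some of them, those consultations fall after the participant's switch-on date but have no exposure. No section says how such a patient is to be handled.

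Two things are at stake. One is the primary ratio, which could be diluted. The other is the clinician-level information that Study 1 is meant to give. Section 10.3 enlarges the sample to look at variability between clinicians, and section 10.6.2 promises an estimate of how the effect varies by clinician. If a code carries several people's work, those results describe codes. For Study 2 the Protocol openly accepts that clinicians within a team cannot be told apart. It makes no such statement for Study 1, although it equates clinician with clinic code there.

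**Working it through.** **Step 1: do the two rules coincide?** They do if every patient on the code is seen by the participant. Let f be the share of patients on the code seen by colleagues without MiADE. The Protocol gives no value for f, so it is an assumption throughout.

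**Step 2: the plan's effect size.** Section 10.3 uses 62% to 70%, with 549 problems per group and 8.8 problems per patient. It states neither the significance level nor the power. Assuming two-sided 5% and 80% power, with pooled variance under the null:

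n = [1.96 × √(2 × 0.66 × 0.34) + 0.8416 × √(0.62 × 0.38 + 0.70 × 0.30)]² / 0.08² = [1.3130 + 0.5618]² / 0.0064 ≈ 549.2

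This is 549, or 550 rounded up; the unpooled version gives 547. Then 549 / 8.8 = 62.4 patients. The plan's figure reproduces, and this point does not change it.

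**Step 3: ratio used for illustration.** r = 0.70 / 0.62 = 1.129. This is borrowed from a proportion. The outpatient outcome is a count with no stated effect size, but section 10.3 itself carries the inpatient calculation over to outpatients.

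**Step 4: clinic-code rule, all entries counted.** Assume f is the same before and after switch-on, and that colleagues' patients have the same baseline mean m and do not change.

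- Pre mean = m
- Post mean = f·m + (1 − f)·r·m
- Observed ratio = f + (1 − f)·r = 1 + 0.129 × (1 − f)

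| f (assumed) | Observed ratio |
|---|---|
| 0 | 1.129 |
| 10% | 1.116 |
| 30% | 1.090 |
| 50% | 1.065 |

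**Step 5: clinic-code rule, only the participant's entries counted.** Colleagues' patients now contribute zeros in both periods.

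- Pre mean = (1 − f)·m
- Post mean = (1 − f)·r·m
- Ratio = r

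At f = 30%: 0.70m before and 0.70 × 1.129m = 0.790m after, so the ratio is still 1.129. The zeros cancel as long as f is constant. What does change is the per-patient mean, which is understated by the factor 1 − f, and the variation between units, which would partly reflect how f differs from code to code.

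**Step 6: what this does not show.** I do not turn step 4 into a loss of power. The 549 relates to a proportion, and Study 1 plans far more patients than that calculation needs: 25 clinicians × 20 patients = 500 in four weeks, against 62. The issue is the size and meaning of the estimate.

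**The case against.** The strongest reply is that the operative text already restricts by clinician. The inclusion criterion in 5.1 does so. So does the sentence in section 4 that says how the outcome is counted, which directly follows the one naming linked clinics. Section 9.4 describes the extract by treating clinician, and section 9.1 is a list of personal data held, not a definition of the analysis set. Extracting by clinic code and then keeping only the participant's own patients would satisfy every section. The own-list requirement also explains why 10.6.2 puts clinic code in brackets after clinician: as a proxy.

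Much of this stands. A reader might infer that colleagues' patients are in fact counted as MiADE-exposed. The documents do not support that: they nowhere describe shared lists, trainees on a participant's list or two participants under one code, and the formal criterion would exclude such patients. A reader might also infer that counting only the participant's entries leaves the bias in place. Step 5 shows that it does not when the share is constant, and nothing in the Protocol suggests that the share changes.

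The reply does not remove the inconsistency. Having one's own list does not mean that nobody else sees patients on it. Nor is this a detail left open for a later plan: the Protocol already fixes the population, the extract and the cluster unit, and fixes them differently.

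**Conclusion.** The Protocol does not settle which rule defines the Study 1 records, and its extract and primary model use a unit different from the one at which MiADE is enabled. Dilution towards 1 is possible, not demonstrated. It needs three conditions together: the clinic-code rule is applied, colleagues see patients under that code, and all entries are counted. Under those conditions, and the assumptions in step 4, an illustrative ratio of 1.129 becomes 1.116, 1.090 or 1.065 at an assumed 10%, 30% or 50%. With no sharing the effect is nil. If only the participant's entries are counted and the share is constant, the ratio is intact, but the per-patient mean and the between-clinician variability are those of clinic codes. This is a modest point, worth correcting because the correction is nearly free.

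**What to change.** Keep the 5.1 criterion as the single rule, and align to it the Study Summary inclusion row, the linked-clinics sentence in section 4, the extract description in 9.1 and the model in 10.6.2. In all three periods, restrict Study 1 to consultations whose recorded encounter clinician matches the participant's EHR login, which section 7.2 already has on the study database. Use that login, not the clinic code, as the random-effect unit. Matching on the encounter clinician, not on who wrote the note, stays within 5.1: a note-author rule would drop patients whom the participant saw but someone else documented.

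The cost is a wording change and one extra field or filter in the extract, with no new data collection from participants. Where lists are shared there will be fewer records than under a clinic-code extract, by the share that colleagues see.

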and analysis:	number per patient of problems, medications and allergies recorded in structured data by the clinician.
	Outpatient observation substudy: comparison (pre- and post- intervention) of proportion of problems, medications and allergies recorded in structured data per patient, with manual review of free text clinical notes considered the 'gold standard'. Descriptive summary statistics will be used to describe the participant demographics for observations and interviews, and qualitative results will be analysed using thematic analysis mapped to the theoretical domains framework.
	Inpatients: comparison (pre- and post-intervention) of proportion of ICD-10 coded diagnoses for hospital admission which have a corresponding structured problem list entry.
FUNDING & OTHER	
Funding	National Institute of Health Research
Other support	Support from the UCL/UCLH NIHR Biomedical Research Centre and the Clinical and Research Informatics Unit
STORAGE of SAMPLES / DA	ΓA (if applicable)
Human tissue samples	Not applicable
Data collected / Storage	The MiADE system will be implemented wholly within the hospital (UCLH) network. All research data will be stored on UCLH servers or in the UCL Data Safe Haven.
KEY STUDY CONTACTS	
Committees	The overall NIHR funded project of which this study is a part is overseen by the MiADE steering committee. The project co-leads ([name] and [name]) jointly chair the MiADE steering committee.
Sub-contractors	None
Other relevant study personnel	Project co-lead and Chief Research Information Officer, UCLH: [name] Lead for clinician engagement: [name] Software developers: [name], [name] Natural language processing expert: [name] Clinical data standards lead: [name] Clinical safety and evaluation of digital health interventions: [name] Human-computer interaction expert: [name]

KEY ROLES AND RESPONSIBILITIES

SPONSOR: The sponsor is responsible for ensuring before a study begins that arrangements are in place for the research team to access resources and support to deliver the research as proposed and allocate responsibilities for the management, monitoring and reporting of the research. The Sponsor also must be satisfied there is agreement on appropriate arrangements to record, report and review significant developments as the research proceeds, and approve any modifications to the design.

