3.3 Outcome measures/endpoints

Primary outcome measures:

Study 1 (outpatient): Number of structured entries for diagnoses, medication and allergies recorded by the clinician in outpatient consultations.

Study 2 (inpatient): The proportion of ICD-10 coded billing diagnoses for which a similar SNOMED CT concept is present in the problem list for inpatients, evaluated at the point of discharge.

Secondary outcome measures:

- The proportion of structured data items suggested by MiADE that are accepted by the clinician for entry into the structured record.
- Computing time required per consultation note.
- Clinician and patient perceptions of the MiADE system.
- Changes to consultation workflow or process as a result of using the MiADE systems

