10.1 Primary outcome

Study 1 (outpatient): The primary outcome is the difference in the mean number of structured problem list, medication or allergy entries, comparing the time periods with and without MiADE switched on.

Study 2 (inpatient): The primary outcome is the difference in the proportion of ICD-10 discharge diagnoses with a corresponding structured problem list entry, comparing the time periods with and without MiADE switched on.

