10.3 Sample size calculation

Based on a prior audit [15], 62% of problem list entries were entered as structured data and there were mean 8.8 problems per patient. In order to detect an increase from 62% to 70%, 549 problems are required in each group, which is 62 patients (assuming 8.8 problems per patient). This study aims to recruit at least 5 inpatient teams who would each discharge at least one inpatient per day, giving 100 patients in a 4-week period.

For outpatients, assuming each clinician sees 5 new patients each week, they will see 20 patients in a 4 week period. Using the same calculation as for inpatients, a sample size of only 5 clinicians is required to investigate the primary endpoint. However, a larger sample (target = 25) will be used in order to assess variability between clinicians.

For the patients in the qualitative substudies, there is no technique for formal sample size estimation. The number of observed clinicians (5 for inpatients and 5 for outpatient) and number of outpatient observations pre and post MiADE (2 per clinician per phase) has been selected to have a high probability of demonstrating potential themes. Using the method of Potts et al. [17], with a sample size of 5, assuming random sampling, there is 83% probability of surfacing a theme exhibited by 70% of the population.

The maximum number of clinicians to be recruited has been set at 100 according to the specification of the NLP server intended to be used for this trial.

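### The protocol gives two different outpatient primary outcomes, entries recorded by the clinician and all entries on the patient's lists; the second dilutes the planned ratio towards 1

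*Protocol*

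**What the plan says.** Two places attribute the outpatient outcome to the clinician. Protocol Section 3.3 gives it as "Number of structured entries for diagnoses, medication and allergies recorded by the clinician in outpatient consultations". The Study Summary, under statistical methodology, compares the mean "number per patient of problems, medications and allergies recorded in structured data by the clinician".

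Section 4 (Study 1) is the only place that says how the count is obtained: "The crude number of entries per patient in the problem list, medication record and allergy record will be calculated". The rest of that sentence selects the patients, namely those the clinician saw in each interval. It does not select the entries.

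The statistics section leaves the matter open. Section 10.1 says "The primary outcome is the difference in the mean number of structured problem list, medication or allergy entries", and Section 10.6.2 says "multilevel Poisson regression will be used to calculate the ratio of counts of structured data entries between pre-MiADE and post-MiADE". Neither states whose entries are counted or when they were made.

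Three other statements bear on this:
- Section 5.1 includes "All outpatients seen by the clinician from 2 months before being consented until 2 months after the MiADE system is switched on", whereas Section 10.3 sizes the study "assuming each clinician sees 5 new patients each week".
- Section 6.1 explains that NoteReader compares extracted items with what the record already holds and shows new and existing items separately.
- Section 7.2 states that "Clinician login names for the electronic health record system will be recorded on the study database".

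**The concern.** A patient's problem list, medication record and allergy record can already hold entries when the consultation starts, made at other visits or by other staff. MiADE can only prompt additions. A count of everything on the lists therefore mixes what the intervention can change with what it cannot.

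An analyst following Section 4 would not be measuring the outcome in Section 3.3. The choice affects the size of the main result, because Section 10.6.2 estimates a ratio and a fixed stock of old entries pulls a ratio towards 1. A useful effect could look negligible. Leaving two definitions in place also allows the choice between them to be made after the data have been seen. This is a conflict within the protocol about its own primary outcome, so it is more than detail left to an analysis plan.

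**Working it through.** **The plan's own figure.** Section 10.3 asks for 549 problems per group to detect 62% against 70%. Significance level and power are not stated; I assume two-sided 5% and 80%. With the usual two-proportion formula, n = [1.960·√(2·0.66·0.34) + 0.842·√(0.62·0.38 + 0.70·0.30)]² / 0.08² = 549.2, which is 549 to the nearest whole number and 550 rounded up. Then 549/8.8 = 62.4, against 62 patients stated. The figure reproduces. It concerns an inpatient proportion, however, and gives no outpatient mean count, stock of prior entries or expected ratio, so it cannot settle this point.

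**Inputs for dilution (all assumed).** E is the number of entries already on the lists, taken as 2, 5 or 8.8; the top value borrows the inpatient audit's 8.8 problems per patient. a is the number of entries the clinician adds per consultation, taken as 1. r is the true post/pre ratio of clinician-made entries.

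**Ratio.** Pre mean = E + a; post mean = E + a·r; observed ratio = (E + a·r)/(E + a).

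| E | true 1.50 appears as | true 2.00 appears as |
|---|---|---|
| 0 | 1.50 | 2.00 |
| 2 | 3.5/3 = 1.17 | 4/3 = 1.33 |
| 5 | 6.5/6 = 1.08 | 7/6 = 1.17 |
| 8.8 | 10.3/9.8 = 1.05 | 10.8/9.8 = 1.10 |

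**Difference in means.** (E + a·r) − (E + a) = a(r − 1), which is 0.5 for r = 1.50 whatever E is. Only the noise grows. If counts are Poisson, with equal numbers of patients per period and clustering ignored, the variance of the difference is proportional to (E + a) + (E + a·r): 2.5 at E = 0, 6.5 at E = 2, 12.5 at E = 5 and 20.1 at E = 8.8. Relative to E = 0, the standard error is larger by √(6.5/2.5) = 1.61, √(12.5/2.5) = 2.24 and √(20.1/2.5) = 2.84.

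**Drift with no MiADE effect.** Suppose a returning patient carries one extra retained entry. Let f₀ and f₁ be the shares of returning patients in the pre and post periods. The null ratio is (E + a + f₁·a)/(E + a + f₀·a). With E = 5 and a = 1:
- f₀ = 0, f₁ = 0.3: 6.3/6 = 1.05
- f₀ = 0.3, f₁ = 0.3: 6.3/6.3 = 1.00
- f₀ = 0.3, f₁ = 0: 6/6.3 = 0.95

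The drift depends on the shares differing (or on list growth differing between periods), and it can go either way.

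**The case against.** The strongest reply is that the clinician-recorded outcome is the intended one. The objective in Section 3.1, the endpoint in Section 3.3 and the Study Summary all say so. Section 4 is a single descriptive sentence, and its word for the count may only mean a raw number without a gold-standard denominator. Author and timestamp rules for an extract are often left to an analysis plan, and this is a feasibility study. It stands that the protocol has not settled on the whole-list count. The conflict itself remains, because the only computing sentence describes a different variable and the statistics section does not choose between the two.

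A reader might go further and infer four things that the documents do not support:
- **That upward drift is built in.** One patient's list may grow, but patients enter and leave a clinic. The 1.05 above needs returning patients after switch-on and none before it, yet inclusion begins two months before consent. The before-consent versus before-MiADE comparison in Section 10.6.4 might reveal list growth, but could not separate it from a Hawthorne effect.
- **That the sign of the result cannot be trusted.** Dilution moves a ratio towards 1 and cannot reverse it.
- **That the bias can be judged against the ratio implied by 62% to 70%.** That is an inpatient proportion, not a ratio of new outpatient entries.
- **That clustering by clinic code misattributes entries.** Section 5.1 requires clinicians to have their own clinic list, and Section 10.6.2 uses the code only for clustering.

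It is also fair to say that counting only new entries has a weakness of its own: problems entered at one visit leave fewer to enter at the next, which could lower post-period counts in returning patients.

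**Conclusion.** The concern holds as an unresolved contradiction in the outpatient primary outcome, with dilution as its consequence if Section 4 is followed. On the ratio scale of Section 10.6.2, and assuming one new entry per visit and 2 to 8.8 prior entries, a true 1.50 would be reported as about 1.17 to 1.05. The direction of the dilution is certain whenever prior entries are counted and the true ratio differs from 1. Its size is not known, because the protocol gives neither quantity for outpatients. The difference in means named in Section 10.1 keeps its size but loses precision. Drift from returning patients or list growth is a possibility of unknown size and direction, and it is not part of the conclusion.

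**What to change.** Align Sections 4, 10.1 and 10.6.2 with Section 3.3 and the Study Summary on one definition: new problem, medication and allergy entries filed under the participating clinician's login at the consultation, excluding entries already present. Count each patient's first consultation in each period. Add a sensitivity analysis that leaves out patients seen in more than one period, because new-entry counts can fall at later visits. Keep the whole-list count as a descriptive secondary outcome.

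The cost is modest. Logins are already to be recorded (Section 7.2) and audit logs are already to be used for acceptance of suggestions (Section 10.6.3), so no new data collection from clinicians or patients is needed. The extract must carry the user and time of each entry. Counts will be smaller and contain more zeros, and the model will have to cope with that.
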